The educational intervention includes three teaching seminars on days 7, 30 and 90. All seminar days have a similar overall structure with a focus on hands-on training and the individual participant's development of scanning competences. However, the teaching aims are different on each seminar which means different focus in the teaching and different activities between seminar days.

[figure not shown]
Teaching seminar 1

The aim of the first teaching seminar is to give participants first-hand experiences with performing POCUS scans and to create a foundation of knowledge and experience which is to be further developed in the coming months. Furthermore, the participants will learn to perform five of the POCUS scans in the selected curriculum.

The teaching seminar will start off with a short lecture summarizing the theoretical foundation for using POCUS and the participants preparation. The teachers will summarize the results of the motivational descriptions and address questions, barriers and concerns raised by participants. Afterwards, a short lecture will follow introducing basic transducer manipulation and image optimization. The participants are then introduced to the five selected POCUS modalities in a short lecture summarizing the fundamentals of the five scans. The participants are then divided into small groups of four participants based on their POCUS experience as declared in the prior assignment. Participants working in the same practice, will be separated into different group to ensure a good group dynamic. The small groups will now circulate between hands-on workshops (Figure 5). Each hands-on workshop will focus on one scanning modality. At the workshop, a

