Outcomes to assess the effectiveness of the intervention:

Following the use of POCUS in the general practice consultations the GPs will follow normal procedures for registration of activities in general practice using remuneration codes, fee-specific codes for using POCUS, and referrals in the medical record system. Prior to this study 11 fee-specific codes for 11 different POCUS examinations will be installed in the medical record system. The Primary Sector Data Provider Platform (PLSP) will develop an algorithm that allows for the following data extraction on each participating GP in a given time frame: (1) number of POCUS examinations performed, (2) number of referrals, and (3) number of consultations (outcomes E1-3). PLSP will deliver monthly aggregated data for each participating GP from baseline to 24 months after baseline. These continues data will be summarized to demonstrate variation over time.

For the registration of the clinical effect of POCUS use in the consultation (outcome E4), we will use an adapted version of a questionnaire used in a previous cohort study²⁴. The GPs will be asked to specify the following for each POCUS examination: (1) organs/structures examined with POCUS (drop down menu or free text), (2) whether POCUS use entailed a change in diagnosis (yes/no), (3) whether POCUS use entailed a change in referral (yes/no), (4) whether POCUS use entailed a change in treatment (yes/no), (5) whether POCUS use entailed a change in diagnostic certainty for the GP (yes/no), (6) whether POCUS use was helpful for the GP in terms of making a decision for patient management (5-point Likert scale), (7) whether POCUS use was helpful for the GP in terms of arriving at a diagnosis (5-point Likert scale). GP will assess the questionnaire immediately after performing POCUS during consultations in clinical practice. These categorical data will be collected for each participating GP from day 7 to day 372.

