Prior to the study, these questionnaires were tested for face validity in four focus groups with 18 POCUS using GPs (unpublished materiel). The Cohen's 10-item Perceived Stress Scale includes ten items about the frequency of stress-related feelings and thoughts. Each item is rated from 0 (never) to 4 (very often). Previous research has reported a sum score of ≥ 18 to be a high level of stress²⁵. The Warr-Cook-Wall Job satisfaction Scale includes 9 sub-items measuring facets of job satisfaction and one overall item rated on a scale from 1 (extreme dissatisfaction) to 7 (extreme satisfaction). In previous research²⁵ a cut-off on the overall item of ≤ 3 has been used to identify low job satisfaction. The Maslach Burnout inventory consists of 22 items exploring the following three burnout dimensions: (1) emotional exhaustion (9 items) characterised by depletion of emotional resources, (2) depersonalisation (5 items) characterised by emotional detachment from people related to work including patients and (3) personal accomplishment (8 items) including perceived value of work and self-efficacy. All dimensions are rated on a scale from 0 (never) to 6 (every day). A sum score is calculated for each dimension. The GP questionnaire will be distributed to participating GPs prior to the third teaching seminar (day 37, at the end of the educational intervention).

Participants characteristics

On the first teaching seminar (day 7) the following participant characteristics will be collected: Age (years), gender (M, F, other), previous use of ultrasound (number of months with regular use), previous ultrasound courses of minimum 1 day duration (yes/no), scanner type (low range, mid-range, high end), type of practice (collaboration, partnership, solo), location of practice (urban, rural, mixed), number of patients assigned to the practice, number of GPs working in the practice.

From PLSP, we will receive the following aggregated data on patients (age, gender) calculated based on patient ID in the medical records in the clinics (CPR numbers). These data are extracted and transferred to CAM AAU anonymously.

13 Time schedule

We will invite participants from two PLO-e ultrasound course to participate:

Teaching seminars course 1: August 31st and September 28th and November 30th 2022

Teaching seminars course 2: September 6th and October 10th and November 29th 2022

Data collection participants in course 1: August 24th 2022 to November 30th 2024.

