Data collection participants in course 2: August 30th 2022 to November 30th 2024.

14 Sample size

This is accompanying research and as such no formal sample size calculations are made. Our potential study population is 36 GPs, who have signed up to participate in an ultrasound course organized by PLO-e. We expect a participation rate of 66% corresponding to 21 GPs. Previous cohort studies from Danish general practice have shown that GPs' average use of POCUS corresponds to once a day. With a data collection period of 24 months for participants corresponding to 200 working days, we expect approximately 8400 POCUS registrations in this study.

15 Recruitment

Two ultrasound courses delivering the educational intervention have been included in PLO-e's course catalogue for 2022 and as such all GPs working in Danish general practice has had the opportunity to sign-up for the courses. PLO-e has handled the participant recruitment and registration based on a first-come-first-served principle as well as the financial and practical aspects of organizing and executing the courses. The two ultrasound courses have a total of 36 available spots and all 36 participants are offered the opportunity to participate in the data collection for this study. However, not all participants will be offered financial compensation for participating in the study, as a collective agreement between the Danish regions and the association of GPs only allows for those GPs with in longest distance to a radiology department to have a free course attendance and a fee for performing POCUS during the data collection.

The offer to participate in the study is made upon registration to the course and repeated at the first webinar (day 1). At the webinar participants are informed about the research project and written information about the project including a consent form is distributed to participants. The signed consent forms are collected from participants on the first training seminar (day 7).

Assignment of interventions

16a Allocation Sequence generation

n/a

16b Allocation concealment mechanism

n/a

16c Implementation

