The data management will follow the rules of the General Data Protection Regulation (GDPR) and the Danish Data Protection Agency. All study data will be stored on a secure server at Aalborg University. Questionnaire data will be collected using the online platform SurveyXact (Rambøll, Aarhus, Denmark). A data management agreement has been made between Rambøll and Aalborg University. At the end of the data collection, data will be moved from SurveyXact to Aalborg University's server.

Register data will be collected by PLSP. Data management agreements between PLSP and CAM AAU will be made prior to the collection of data. PLSP will receive data from the different IT suppliers for the general practice clinics. Data management agreements between the IT suppliers and PLSP as well as the GP clinics and the IT suppliers already exists. For this specific study, we will develop an instruction for the GPs to incorporate in the existing data management agreement prior to the collection of data.

All patient-related data will remain in the GPs clinics until the end of the educational intervention (day 97). No data will be transferred to CAM AAU before legal approval by the health authorities has been obtained.

20a Statistical methods for analysing primary and secondary outcomes.

All statistical analyses will be performed using STATA version 17 (StataCorp, Texas, USA) and analyzed according to a predefined statistical analysis plan, which will be uploaded to clinical Trials.org prior to the analysis of data (24 months after baseline). Data will be summarized and reported using descriptive statistics.

For effectiveness related outcomes E1-E5, frequencies and variance are reported as mean and 95% CI or median and IQR depending on the distribution of data. We will use graphic illustrations to demonstrate change over time. To test if changes over time are significant, we will use repeated measures ANOVA analysis.

For outcomes related to the implementation strategy effects (I1-I4) and feasibility of trial methods (F1-F7), we will report proportions as frequencies, while outcomes related to the implementation strategy (D1-D9) will be reported with an average score and outcomes D10-D11 with a summarized estimate on costs. For feasibility related outcome F8, we will report the questionnaire response rate and the corresponding 95% CI.

20b Methods for any additional analyses (e.g. subgroup and adjusted analyses).

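### Section 20a makes no provision for GPs who share a practice: if colleagues enrol, E1–E3 intervals may be too short, and the time test is too liberal only if they share month-to-month changes

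*Protocol*

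**What the plan says.** Section 11a (Teaching seminar 1) sets a rule for composing the hands-on groups: "Participants working in the same practice, will be separated into different group to ensure a good group dynamic". The eligibility criteria (section 10) and the first-come sign-up (section 15) do not restrict a practice to one participant.

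Section 12 defines the data for E1–E3: "PLSP will deliver monthly aggregated data for each participating GP from baseline to 24 months after baseline". The unit is therefore the GP-month. The baseline form asks for the "number of GPs working in the practice" and the type of practice, but nothing links these items to the analysis.

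Section 20a states that for E1–E5 "frequencies and variance are reported as mean and 95% CI or median and IQR depending on the distribution of data". It continues: "To test if changes over time are significant, we will use repeated measures ANOVA analysis". No practice term, cluster-robust variance or multilevel model is mentioned. A predefined SAP is announced but is not at hand.

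Section 14 gives the size: "Our potential study population is 36 GPs" and "We expect a participation rate of 66% corresponding to 21 GPs".

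**The concern.** An ordinary 95% CI for a mean over GPs and an ordinary repeated measures ANOVA both take the GP as the independent unit. Two GPs from one practice may not be independent, for reasons found in the protocol itself. The ultrasound device is required at practice level (section 10). Patients are counted per practice (section 12). Register data come through the IT suppliers of the clinics (section 19). Free attendance and a fee per scan depend on distance to a radiology department (section 15), hence on practice location, and the decision on payment was expected in September 2022, while the courses ran (section 9).

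E1–E3 ask how use, referrals and consultations develop, and how they vary over time and between GPs. If colleagues move together, their data carry less information than two separate GPs would. The interval is then too short, and a common swing in one clinic can count twice as evidence of change. Without a practice level, differences between practices and the sharing-out of scanning inside a practice are both reported as variation between GPs.

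**Working it through.** **Plan's own figures.** 0.66 × 36 = 23.76, so 24 GPs, not 21; 21/36 = 58.3%. The protocol's "corresponding to 200 working days, we expect approximately 8400 POCUS registrations in this study" needs 21 × 400 = 8400, that is 200 working days per year for two years; 21 × 200 = 4200. These slips are separate from the present point. I use N = 21 as stated.

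**Assumptions.** The documents give no number of shared practices, no within-practice correlation and no significance level. I assume 1 or 3 same-practice pairs, correlations of 0.05 to 0.5, and 5% (from the 95% CI).

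**Interval of a mean.** With practices of size m and within-practice correlation ρ, the variance of the mean is multiplied by

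D = 1 + ρ(Σm²/N − 1).

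- 1 pair: Σm²/N = (4 + 19)/21 = 1.095. √D = 1.002 at ρ = 0.05 and 1.024 at ρ = 0.5.
- 3 pairs: Σm²/N = (3 × 4 + 15)/21 = 1.286. √D = √1.014 = 1.007 at ρ = 0.05 and √1.143 = 1.069 at ρ = 0.5.
- 3 pairs among 24 GPs: Σm²/N = (12 + 18)/24 = 1.25. At ρ = 0.5, √D = √1.125 = 1.061, so the choice of N hardly matters.

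With 3 pairs the correct standard error is thus 0.7% to 6.9% larger than the nominal one. In simulation, the nominal 95% interval of a one-month mean covered 93.6% with 3 pairs and correlation 0.5.

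**Test of change over time.** Write the count of a GP in a month as overall level + month + practice + GP + residual. The ANOVA compares months within GPs. Subtracting each GP's own mean removes the practice term as well as the GP term, so a stable practice effect has no influence on the test. What remains is the part of the residual that colleagues share in the same month; call its share of the residual variance r. Then, with no true change and residual variance 1:

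- expected mean square for month = 1 + r(Σm²/N − 1)
- expected error mean square = (N − that value)/(N − 1)

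With 3 pairs and r = 0.5 these are 1.143 and (21 − 1.143)/20 = 0.993, a ratio of 1.151 instead of 1. A 15% inflation of F matters because the numerator has 23 degrees of freedom.

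I simulated 21 GPs × 24 months with no true change, using the uncorrected F test, 10,000 runs per setting. Rejection rates at nominal 5%:

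| Pattern | Constant practice effect only (share 0.1; 0.5) | r = 0.1 | r = 0.3 | r = 0.5 |
|---|---|---|---|---|
| 1 pair | 4.9%; 4.8% | 5.5% | 6.2% | 6.9% |
| 3 pairs | 5.0%; 4.9% | 6.4% | 9.2% | 13.0% |

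Runs with no pairs gave 4.8% to 5.5%, so the entry for one pair at r = 0.1 is not distinguishable from nominal.

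**How many pairs are plausible?** If course attendees consent independently, both members of a pair enrol with probability 21/36 × 20/35 = 0.33. An expectation of 3 study pairs then needs 3/0.33 = 9 course pairs (18 of 36 places). If colleagues always decide together, it needs 3/0.583, or about 5 course pairs. Three pairs is an illustration, not an estimate.

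**The case against.** The strongest objection is that handling of shared practices is ordinary SAP detail, and the SAP is not shown. This stands in part: the SAP may add a practice level. But section 20b explicitly defers its detail to the SAP, whereas section 20a already names the test and the intervals. The point concerns a method the protocol states, in a setting the protocol itself provides for.

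Second, the grouping rule covers course attendees and gives no number. A reader might infer that several GPs from one practice are expected in the study. The text does not say so; it says what happens if colleagues attend. With no shared practice among those who consent, there is no effect at all.

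Third, a reader might infer that practice clustering as such makes the ANOVA reject too often. It does not, as the constant-effect column shows. Inflation needs shared month-to-month variation. The location-dependent payment decision and clinic-level data extraction make this plausible, but nothing in the documents demonstrates it.

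Fourth, the direction is not certain. Colleagues who cover each other's leave or pass scans to one partner may have negatively correlated months. That would make the test conservative and, if it dominates, the interval too long.

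Finally, little hangs on the test. There is no formal sample size calculation, the progression criteria in section 16c do not use the ANOVA, and where a median with IQR is reported there is no interval to correct. This limits the consequence; it does not supply the missing provision.

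**Conclusion.** The point holds in conditional form. The protocol allows for GPs who share a practice, sets no limit of one per practice, and fixes GP-level intervals and a GP-level time test for E1–E3 that treat GPs as independent.

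The size rests on assumed pairs and correlations. With 3 pairs among 21 GPs, the effect on the interval is modest (1% to 7% in the standard error). The effect on the time test ranges from slight to material (6% to 13% at a practice-by-month share of 0.1 to 0.5), and it is absent if the practice effect is constant.

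Two further readings are tempting but unsupported. Much larger figures can be produced: with 10 pairs and a share of 0.5 the rejection rate is 43.7%. But that has 20 of 21 GPs paired, for which the documents give no basis. Nor do the adoption, fidelity and sustainability outcomes (I1, I2, I4) need corrected intervals: section 20a reports them as proportions and plans no interval. The change is worth making because it is cheap and the exposure is unknown until practices are counted.

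**What to change.** In section 20a:

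- Keep a practice identifier for each GP, which the organisers need anyway to apply the grouping rule, and report the number of practices and of GPs per practice.
- Where practices are shared, compute the E1–E3 intervals with practice as the cluster, by bootstrap over practices or a small-sample cluster-robust variance.
- Test change over time through a low-dimensional contrast, such as a trend or a few periods, with practice as the resampling or clustering unit. An unrestricted test of all months is not workable: with 3 pairs there are 15 + 3 = 18 practices against 23 monthly contrasts. A full practice-by-month variance model would rest on the three pairs alone.
- Still report variation at GP level, since E1–E3 ask for it, and show within-practice differences alongside it where colleagues enrol.

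If no practice contributes more than one GP, a sentence saying so is enough. The cost is a few lines of text, one identifier, slightly wider intervals and a little more analysis work. A trend or period contrast also gives up sensitivity to irregular monthly patterns, which the planned graphs would still show.

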3. A wall for sharing information between all participants. Here there is a group chat function, where participants may share experiences and reflections with each other the learning process. The teachers may also engage in this ongoing debate. Videos, documents, links etc. may be uploaded or posted and shared here and all participants will have the opportunity to comment on uploads and posts. Notifications for the participants are also posted here.
4. Invitations to webinars with the teachers, where tips and tricks are shared based on the participants uploaded or returned comments, feed-back, uploads and logbook registrations.
5. A document where notes can be shared between the participants during webinars or teaching seminars.
6. Link to the individual assignments to be completed by participants during the learning process. The teachers on the course have the opportunity to comment and respond in the assignment.
7. A link to an online logbook where the individual participant can note conducted POCUS examination during the learning process (date, type of POCUS, focus during the examination, reflections afterwards). A template specifies the number of examinations recommended at each phase in the educational intervention.
8. A direct chat opportunity with the teachers, where participants can have access to guidance and support from the course teachers. It is also possible to upload scanning images or videos for review by the teachers.
9. The individual structured feedback for all scanning modalities collected at teaching seminar 2 and 3.
10. Access to Pre/post self-quizzes before and after each training seminar and access to the results.

Participants will receive a notification by email or on their phones, when there is activity on the online platform. The overall purpose of this online platform is to support the participant in the continuous learning process. We aim to create awareness about the learning process, individual focus points and goals, the importance of training and gaining experience, and to make guidance available when difficulties/problems are encountered.

Teaching seminars (day 7, 37 and 97)

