of training without having to draw conclusions based on their scans. As such, participants are in this phase encouraged to treat patients as usual without taking scan results into account.

Participants are also encouraged to train examinations on volunteers e.g. family members, as the goal in this phase is to perform as many examinations as possible.

During the three weeks between the two teaching seminars, participants are encouraged to register all POCUS examinations in their individual logbook and note reflections and questions that occur during this process. It is recommended that participants aim to perform a minimum of three POCUS examinations of each scanning modality in the curriculum and upload one POCUS examination of each scanning modality for review by the teachers (assignments 2, 3, 4, 5, and 6). Midway in the practice phase (day 20), participants will be invited to participate in a half-an-hour webinar. In this webinar, one of the teachers will go through some of the encountered problems and difficulties uploaded or posted on the online platform. Participants will also have the opportunity to ask questions.

Prior to the second teaching seminar, *motivational description 2* is sent to the participants. In this assignment participants have to register their specific focus points and individual learning goals for the second seminar as well as any questions they may have to the teachers.

A specific pre-self-quiz will be available before teaching seminar 2. This self-test will assess basic knowledge of the five POCUS scans introduced at the first teaching seminar and prime the participants for the learning objective of the second teaching seminar.

Teaching seminar 2

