This phase in the learning process is considered and articulated as a developing phase, where participants continue to develop their scanning skills and routines. The participants are encouraged to use POCUS examinations on all patients with relevant clinical conditions suited for POCUS and to work with the integration of POCUS into their clinical practice and medical decision making. It is important in this phase that the participants develop routines and become comfortable performing POCUS examinations. During the eight weeks between the teaching seminars 2 and 3, participants are encouraged to register all POCUS examinations in their individual logbooks and note reflections and questions that occur during this process. The participants will still have the opportunity to consult the teachers during this phase by uploading questions, images or videos to the online platform. It is again recommended that participants perform a minimum of three POCUS examinations on patients within each scanning modalities during the eight weeks and that participants upload at least one POCUS examination of each of the five new scanning modalities for review and feed-back (assignments 8-12).

During the eight weeks, participants will be invited to participate in two half-an-hour webinars (on day 50 and 75). At these webinars, one of the teachers will go though some of the encountered problems and difficulties uploaded or posted on the online platform and present images and videos of common pathologies with the 10 selected POCUS modalities. Participants will also have the opportunity to ask questions and the teacher will have an ultrasound device and a volunteer available for live POCUS demonstration.

Before the third and final teaching seminar, the participants will be asked to complete a pre-self-quiz and to send in a list of questions or topics that they want included in the final teaching seminar (assignment 13).

[figure not shown]
Teaching seminar 3

Before the final teaching seminar, the teachers will prepare feedback for each participant based on the information gathered about each participant, i.e., from notes in the logbook, the uploaded scans, impressions from teaching seminars, the correspondence in the chat function, etc.

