GP registrations: For the GPs' registration of POCUS effect in the consultation (outcome E4), GPs will use paper registrations in logbooks during the educational intervention (day 7 to 96). Here the registrations are made for the GPs own purpose as part of the learning process. Following the educational intervention, we will ask the GPs to continue making these registrations with the purpose of research, using a QR code to access an online questionnaire. The paper registrations will be collected by the research team at the third teaching seminar (day 97) while the online-questionnaire data are collected continuously from day 97 to 372.

For the reporting of anonymously unwanted cases, GPs will have a QR code and a link for an online questionnaire (outcome E5). These data are collected prospectively continuously during consultations from the day 7 – day 829.

GP questionnaire: For the pilottest of a cross-sectional questionnaire exploring burnout, stress and job satisfaction at 3 months (outcome F8), an online questionnaire will be distributed to participants following the third seminar day and a possible reminder will follow after two weeks. The questionnaire collecting background characteristics on participating GPs will be distributed on the first teaching seminar (day 7).

Online platform: For the evaluation of participant adherence (outcome I2) and reach (outcome I3) we will use the registrations on the online platform (Microsoft Teams) supporting the educational intervention. These are collected retrospectively at the end of the educational intervention (day 97).¹²

Process evaluation questionnaire: For the evaluation of implementation of the educational intervention (outcomes D1-11) a questionnaire will be distributed to teachers and participants following the educational intervention (day 97).

18b Data collection - Plans to promote participant retention and complete follow-up

During the study, the principal investigator is available for consultation for the participating GPs in order to resolve any problems or obstacles. Reminders will be sent to the participating GPs reminding them to scan patients and contact the research team in case of problems.

19 Data management

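### A first-year change in E4's referral and treatment items could reflect the end of the practice-phase advice and the other changes at seminar 2, not growing clinical impact

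*Protocol*

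**What the plan says.** All references are to the protocol.

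- **Objective (section 7).** E4 asks how the effect of POCUS on decisions and patient management, as GPs report it, develops over the first year.
- **Window and items (section 12).** "These categorical data will be collected for each participating GP from day 7 to day 372". For each scan the GP answers seven items, among them "3) whether POCUS use entailed a change in referral (yes/no), (4) whether POCUS use entailed a change in treatment (yes/no".
- **Source (section 18a, GP registrations).** For E4, "GPs will use paper registrations in logbooks during the educational intervention (day 7 to 96", as part of their own learning. The research team collects these at seminar 3. After that the GPs register "with the purpose of research, using a QR code to access an online questionnaire".
- **Advice between seminars 1 and 2 (section 11a, practice phase).** "participants are in this phase encouraged to treat patients as usual without taking scan results into account".
- **Advice between seminars 2 and 3 (section 11a, developing phase).** GPs are encouraged "to work with the integration of POCUS into their clinical practice and medical decision making".
- **Test (section 20a).** For E1-E5, "To test if changes over time are significant, we will use repeated measures ANOVA analysis". No E4 time bins and no analysis start later than day 7 are stated.
- **Logbook (section 11a, online platform, item 7).** "A link to an online logbook where the individual participant can note conducted POCUS examination during the learning process". The fields named are date, scan type, focus and reflections.

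**The concern.** The referral and treatment items ask whether the scan changed what was done for the patient. A GP who follows the practice-phase advice has little basis for answering yes, however useful the scan was. The advice is reversed at seminar 2. The first stretch of the series may therefore be held down by the course itself, and that stretch anchors any test of change from day 7.

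E4 is meant to show how clinical impact develops. A significant ANOVA on these two items could be read as impact growing with experience when it shows only that GPs moved from training use to clinical use. The diagnosis item may be exposed in the same way. The certainty and helpfulness items can be answered without acting on the scan, so they are much less affected.

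**Working it through.** **1. Window.** 372 - 7 = 365 days, which reproduces the stated first year (366 days counting both ends).

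**2. Length of the exposed stretch**, from the seminar dates in section 13:

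- Course 1: 31 August to 28 September = 28 days; 28/366 = 7.7%.
- Course 2: 6 September to 10 October = 34 days; 34/366 = 9.3%.

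Cutting at 30 days would leave 34 - 30 = 4 practice-phase days in the course 2 test, so the cut has to follow the actual dates.

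**3. What changes at each boundary.**

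| Boundary | Changes |
|---|---|
| Seminar 2 | Advice on using scan results is reversed; five new modalities are taught; GPs receive assessed feedback |
| Seminar 3 | Paper registrations for learning give way to an online questionnaire for research |

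All participants in a course cross each boundary on the same day, and there is no comparison group. The data cannot separate the parts of the seminar 2 step. Only the stretch from seminar 3 to day 372 has constant advice, curriculum, instrument and purpose. Seminar 3 falls 91 days after seminar 1 in course 1 (31 August to 30 November) and 84 days after in course 2 (6 September to 29 November). That leaves 365 - 91 = 274 and 365 - 84 = 281 days.

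**4. Scans per GP-month.** Section 14 expects 8400 registrations from 21 GPs over 24 months: 8400/21/24 = 16.7. Its own 200 working days at one scan a day give 21 x 200 = 4200, or 4200/21/24 = 8.3. Both rates are shown because section 14 does not settle which applies.

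**5. Chance that the ANOVA detects an assumed drop.** This was simulated with 21 GPs, yes-proportions per GP and bin, a 5% level and 2000 runs per cell, with a flat true proportion outside the practice phase. Assumptions not in the protocol:

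- monthly or quarterly bins;
- a later rate of 20% or 50%;
- a between-GP SD of 0.7 on the logit scale;
- a practice phase covering 73% or 100% of month 1.

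Ranges run over the four rate-by-coverage combinations.

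| Scans per GP-month | Assumed drop | Monthly bins | Quarterly bins |
|---|---|---|---|
| 8 | 25% | 8-43% | 7-25% |
| 8 | 50% | 26-99% | 17-77% |
| 17 | 25% | 15-87% | 10-49% |
| 17 | 50% | 64-100% | 30-98% |
| 17 | none | about 5% | about 5% |

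A second run used SD 0.6, month 1 fully covered, monthly bins and 4000 runs. At 8 scans and a 25% drop it gave 14%, 25% and 45% for later rates of 20%, 35% and 50%. With month 1 left out, rejection is 4-6%; on months 4-12 alone it is also 4-6%.

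**6. Does the logbook carry the items?** Sections 12 and 18a treat the day 7-96 registrations as E4 data. Section 11a names four fields, none of them a yes/no item on referral or treatment, and calls the logbook online where section 18a says paper. If the items are absent, this problem does not arise, but then the day-7 start in section 12 cannot be met for E4.

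**The case against.** **The test is not invalid.** A reader might infer that the percentages above are an inflated type I error. They are not. In those simulated data the reported proportion really is lower in the practice phase, so a rejection detects a real difference. A low first month is also a true description of what GPs report, and the practice phase belongs to the intervention. This objection stands in full; what remains is a risk of misreading.

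**The step cannot be credited to the advice alone.** That is another tempting inference. Seminar 2 also brings five modalities and feedback, so scan mix and skill change at the same moment. This stands. It does not rescue the reading as growing impact over the year, because a step at a course event is still not a trend in clinical use.

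**The advice is encouragement only**, and GPs with earlier ultrasound experience may enrol, so the drop could be small. This stands, and the size is unknown.

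**The SAP may define bins and phases.** It may, and section 20a refers to it. But the protocol itself fixes the day-7 start and names the test for E4, and nothing in it separates the practice phase. If the SAP does so, only the logbook wording remains to be settled.

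**The logbook may hold no E4 items.** This is a genuine condition on the point and is kept as one.

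**Conclusion.** The point holds as a conditional risk of misinterpretation, of low to moderate weight. If the logbooks carry the E4 items, a significant first-year change in the referral and treatment items could arise from the end of the practice-phase advice together with the other changes at seminar 2, and would not by itself show growing clinical impact.

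The size depends on how far GPs follow the advice, the base rate and the time bins, none of which the protocol states. At about 8 scans per GP-month and an assumed 25% drop, the chance of detecting that drop is roughly 7-43%. It is higher with more scans or a larger drop.

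The documents do not support saying that the ANOVA is wrong in itself, that the advice alone would explain a change, or that all of E4 is affected. Nor is the training advice in question here; the point concerns only how E4 is analysed and read.

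**What to change.** 1. Keep the full first-year description of E4, but report it by phase: practice phase, seminar 2 to seminar 3, and after seminar 3. Set the boundaries at each course's actual seminar dates in section 13.
2. Start the test of change for the referral and treatment items after seminar 2. Do the same for the diagnosis item if it is judged exposed.
3. That test still crosses the switch of instrument and purpose at seminar 3. Repeat it on seminar 3 to day 372, and describe a change as growing impact only if it also appears there.
4. Reconcile section 11a (online platform, item 7) with sections 12 and 18a: is the logbook paper or online, and does it hold the seven E4 items?

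**Cost.** Wording in the protocol or SAP. For the exposed items, 28 days of data in course 1 and 34 in course 2 leave the test but stay in the description. The repeat on the later stretch uses about nine months of data and so has less power to show an early change.
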